More recently, Gettings et al.[8] conducted a retrospective study of patients with posttraumatic AKI and stratified patients on the basis of timing of the initiation of dialysis into "low" and "high" degree of azotemia groups using a BUN cutoff of 60 mg/dl. Mortality rates among patients who initiated dialysis at the lower BUN cutoff was 61%, compared with 80% among those who started dialysis with higher BUN levels ($P = 0.04$).

Additional studies[9, 10] examined the timing of initiation of dialysis for AKI after cardiac surgery and demonstrated a benefit to earlier initiation of dialysis. These studies used a definition of AKI to justify the provision of early dialysis of a urine output <100 ml during the first 8 h after bypass surgery regardless of solute clearance. Demirkilic et al.[9]studied a total of 61 patients; the overall mortality rate in those who were treated with early dialysis was 24%, compared with 56% in control subjects ($P = 0.016$). Elahi et al. [10] reported the results of their analysis of 64 patients with postbypass AKI; the overall mortality rate in

those who were treated with early dialysis was 22%, compared with 43% in control subjects (P<0.05). However, the relevance of these data to nonpostoperative patients or to patients with nonoliguric AKI is unclear.

[figure not shown]
Liu et al.[3] showed that even with adjustment for confounding and selection effects, patients with higher BUN concentrations at the start of dialysis had worse outcomes as compared to those patients with lower BUNs.

Since the initiation of this protocol, we have recruited subjects with early Stage 1 AKI (a 0.3 mg/dL absolute or 50% relative increase in serum creatinine or 0.5 ml/kg/hr of urine output for 12 hours – AKIN Stage 1) to prospectively receive a one-time furosemide bolus. We have recently published our preliminary data describing patient outcomes following the Furosemide challenge [11] This Renal Stress test was prospectively administered to 54 ICU patients (across 2 centers) in the setting of early AKI and was dosed at Furosemide 1 mg/kg for loop diuretic naïve patients (1.5 mg/kg for those who had previous loop exposure). Over the first 6 hours post FST, UOP was able to significantly predict the development of Stage 3 AKI (AUCs 0.82-0.87) as well as a composite endpoint of Stage 3 AKI or In-Hospital Death (AUC 0.74- 0.77). (Table 1) These results were similar to those of a 23 subject

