retrospective cohort from the Southern AKI Network (SAKI-Net) who were noted to have previously received an FST in the setting of Stage 1 AKI: AUC for AKIN-3 (0.83-0.87) and 0.85-0.89 for AKIN-3 or Death. **Figure 1** demonstrates the UOP in progressors (those reaching Stage 3, n=25) and non-progressors (n=52) in the first 3 hours following FST (n=77). **In our 77 subject cohort, total UOP of less than 200 mls during the first 2 hours post-FST was both a sensitive (87.1%) and specific (84.1%) marker for the progression to Stage 3 AKI.[11]** This cutoff of 200 mls remained extremely sensitive for the composite endpoint of AKIN-3 and death (90%) although the specificity did drop (74.2%). Finally and most importantly, the FST was extremely well tolerated with no episodes of hypotension or any adverse event attributable to the diuretic challenge. This stems from the pre-enrollment selection of patients who were euvoemic and stable for FST as deemed by their treating physicians. Additionally, treating teams were given the option to replace urinary losses after FST with the IV fluid of their choosing.

Table 1: Prospective Cohort - FST ROC-AUCs for Progression to AKIN -3 and Composite Endpoint (n=54)		
	AKIN-3	AKIN-3 or Death
One Hour	0.82(0.07)*	0.74(0.08)*
Two Hour	0.87(0.07)*	0.76(0.08)*
Three Hour	0.87(0.07)*	0.76(0.08)*
Four Hour	0.87(0.07)*	0.76(0.08)*
Five Hour	0.87(0.07)*	0.77(0.08)*
Six Hour	0.86(0.07)*	0.76(0.08)*

*p<0.01

Future studies are needed to validate our preliminary data as well as assess the post-hospital discharge outcomes in this cohort. Once the furosemide challenge is validated and we have a method to identify severe early AKI then and only then can we focus on randomized prospective studies on early versus late RRT in patients with AKI.

D. Research Design and Methods

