F. Human Subjects

The study aims to enroll 200 subjects with AKI that are admitted to the hospital. The proposed study requires an intervention as well as collection of human specimens, urine and blood samples. As such, approval from the IRB will be received prior to any study subject enrollment. Identification of study subjects will be determined based on clinical and laboratory tests and without regard to gender or racial/ethnical origin. Subjects will be initially selected for the study based upon their medical histories and laboratory studies

obtained prior to the study, according to the inclusion and exclusion criteria enumerated in Section E of the protocol.

During the subject recruitment, the investigator will explain the study in detail to the patient or their representative (e.g., power of attorney), and provide a copy of the informed consent to the subject for review. If the patient agrees to participate, the IRB approved consent form will be signed. Each patient will receive a copy of the signed consent form. The original consent forms will be stored in the research office at the ICU for record review from authorized parties if needed.

When consent is obtained from a legally authorized representative, a subject's incapacity to consent will first be verified and documented by two physicians, one of whom will be independent of the study team for patients who are unconscious or have documented diagnosis of delirium. In the case of conscious, non-delirious patients, documentation of incapacity to consent will include evaluation by a psychiatrist or psychologist. When subjects who were decisionally impaired at the time of enrollment are informed of study participation the subject will be consented if he/she wishes to continue on the study. The PI, research nurse or member of the research team will consent the subject.

There are no direct benefits for study participation.

G. Risks and Side Effects:

During this study, patients will be given a single dose of furosemide. Furosemide is a diuretic commonly given to patients with AKI. Furosemide has a favorable safety profile. The risks of furosemide administration are as follows: hypersensitivity reactions, volume depletion, hypokalemia, hypomagnesemia, and ototoxicity. In order to mitigate any risk of hypovolemia, patients will be given isotonic saline milliliter for milliliter after the furosemide bolus.

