The patient may be exposed to some risks related to blood drawing. We will collect only five (pre-furosemide, 2 hours post-furosemide, 24 hours post-furosemide, ICU discharge and hospital discharge, . Most of the blood samples will be taken by an intravenous catheter which is commonly used in the ICU for treatment purposes. This method of blood drawing will minimize the risks for any possible side-effects. In case the blood is drawn by a needle procedure, there are possibilities of a bruise and slight pain. Rarely, fainting or infection may occur. In addition to blood samples, we will collect two samples of urine samples for all patients in the study. Each urine sample will be 50 milliliter (10 teaspoons of urine over 24 hours). Collection of urine samples does not carry additional risks for the patient because all patients will have an indwelling bladder catheter as part of their study eligibility.

In addition to specimen samples, clinical and laboratory data will be collected from the medical records. . Patients will sign a release of information form at the time of consent that will permit the study team to contact their outside physicians for any / all relevant lab work collected (comprehensive metabolic panel and any urine studies) – this will be done

to allow for determination of post-discharge kidney function to determine if there was any loss of kidney function following the episode of AKI. All data will be held confidential to the investigator in the study. All names and individual identifiers will be separated from the collected data. If and when the data is published, it will be presented in an anonymous fashion to avoid any violation of patient's confidentiality.

Adverse Events

Adverse Events are negative reactions associated with furosemide not present at baseline: hyper-sensitivity reactions (allergic reactions, e.g. rash), dehydration, electrolyte depletion and tinnitus occurring within 24 hours post dose administration. Non-serious AEs will be reported at the time of continuing review.

A study-treatment related adverse event which fits any of the criteria below, is considered a serious adverse event (SAE):

- Results in death
- Is life-threatening (meaning that the patient was at risk of death at the time of the event; this does not refer to an event which might have caused death if it had occurred in a more severe form)
- Requires in-patient hospitalization or prolongs the existing hospitalization

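### The adverse-event definition reads as a closed list that omits hypotension, so non-serious falls in blood pressure after the bolus have no planned, uniform count

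*Combined protocol and SAP*

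**What the plan says.** - **Adverse events (Section G, Adverse Events).** The definition opens "Adverse Events are negative reactions associated with furosemide not present at baseline". A colon and four items follow: hypersensitivity reactions, then "dehydration, electrolyte depletion and tinnitus occurring within 24 hours post dose administration". The only e.g. sits inside the hypersensitivity item and does not apply to the list as a whole.
- **Serious adverse events (same section).** The rule begins "A study-treatment related adverse event which fits any of the criteria below, is considered a serious adverse event (SAE". The seriousness criteria follow, and the last is an important medical event in the investigator's judgement.
- **Furosemide risks (Section G, opening paragraph).** These are given as "hypersensitivity reactions, volume depletion, hypokalemia, hypomagnesemia, and ototoxicity". Hypotension is not among them.
- **Pilot tolerability (Section C).** The pilot is reported as showing "no episodes of hypotension or any adverse event attributable to the diuretic challenge".
- **Data to be collected (Section D, Statistical Analysis and Study Procedures).** Dialysis, creatinine, urine output, medication and mortality are named; blood pressure is not. Section G adds a general statement that clinical and laboratory data will come from the medical records, without listing items.

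**The concern.** A loop diuretic can lower blood pressure through volume loss, and the pilot report treated hypotension as the event worth naming. The adverse-event rule for the larger study does not carry it over. A site following Section G to the letter could see a moderate pressure fall after the bolus and have no duty to record it as an adverse event. Each site monitors its own conduct (Section I), so any capture beyond the list would depend on local habit.

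Two smaller gaps come from the same sentence. Ototoxicity is a stated risk, but only tinnitus is recordable. Tinnitus is a symptom the patient must report, and Section F provides for enrolling unconscious or delirious patients. Electrolyte depletion is listed without a defining value or a named post-dose measurement, although the exclusion criteria give entry limits for potassium and magnesium.

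At stake is how a low adverse-event count could be read. For hypotension, it would partly reflect what the definition asked sites to record.

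**Working it through.** **Step 1. Is hypotension captured by any stated route?** The plan gives no safety rate or safety sample size, so there is no figure to reproduce. The check is a reading of each route.

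| Route | Does it reach non-serious hypotension after the dose? |
|---|---|
| Adverse-event list | No. Four items, hypotension not among them |
| Dehydration item | In part. It may overlap where the fall is due to volume loss, but it is a different event and has no blood-pressure criterion |
| Serious-event rule | Not clearly. The event must first be a treatment-related adverse event; the important-medical-event criterion might admit a severe case |
| Follow-up variables (Statistical Analysis) | No blood-pressure variable. Medication regimens might show some treated cases |
| Study Procedures | No blood-pressure measurement listed |
| General chart collection (Section G) | Possible, but with no item, definition or window |

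Elsewhere hypotension appears only as an answer option for the cause of AKI in the Physician Assessment survey. No route gives a definition, a window and uniform capture together.

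**Step 2. Which pilot denominator?** Section C says "This Renal Stress test was prospectively administered to 54 ICU patients (across 2 centers". It then adds a 23-patient retrospective cohort (54 + 23 = 77) and reports test performance with the words "In our 77 subject cohort". The tolerability sentence does not say which group it covers, so both are shown.

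**Step 3. Scale: what zero events can exclude.** With 0 of n, the exact one-sided 95% upper bound is 1 − 0.05^(1/n). The upper limit of the exact two-sided 95% interval is 1 − 0.025^(1/n).

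| n | One-sided 95% bound | Two-sided 95% upper limit |
|---|---|---|
| 54 | 1 − 0.05^(1/54) = 5.4% | 6.6% |
| 77 | 1 − 0.05^(1/77) = 3.8% | 4.7% |
| 200 | 1 − 0.05^(1/200) = 1.5% | 1.8% |

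**Step 4. Scale: chance of seeing at least one event.** This is 1 − (1 − p)^n. The documents give no true rate p, so the values below are assumptions.

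| Assumed p | n=54 | n=77 | n=200 |
|---|---|---|---|
| 0.5% | 24% | 32% | 63% |
| 1% | 42% | 54% | 87% |
| 2% | 66% | 79% | 98% |

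The planned 200 patients would say noticeably more about a rare drug-related fall in pressure than the pilot could, provided such falls are recorded. These figures are not a forecast. The 1.5% bound requires zero events, which is unlikely if hypotension from any cause is counted in a cohort whose morbidity and mortality the plan itself calls extremely high.

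**The case against.** The strongest reply is that this is not a safety trial. The aims concern early prediction of the course of AKI, physician judgement against biomarkers, and three-year outcomes. The primary analysis is reclassification. The stated wish to replicate the pilot's success opens the sample-size section, which deals with predicting Stage 3 AKI. This stands: no passage promises to confirm tolerability, and any hypotension count would be descriptive.

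A reader might infer that the trial cannot confirm the pilot's safety claim, or that its definitions guarantee a clean record. The documents support neither. The four listed reactions remain reportable. The pilot statement also covers any attributable adverse event, so that part can still be checked for the listed reactions. Severe hypotension could surface as dehydration, in chart or medication data, or through the important-medical-event criterion.

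It can also be said that the design lowers the risk. Under-resuscitated and bleeding patients are excluded, as are those with prior hearing loss or receiving aminoglycosides, and matched saline is the default for six hours. That bears on how often events occur, not on whether they are counted, and the treating team may give less saline.

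Finally, hypotension in ICU patients often has other causes, and without a control group attribution is a judgement. That is correct. It limits what a rate would mean, but it is not a reason to leave the event undefined.

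**Conclusion.** The point holds as a gap in recording. Read plainly, the adverse-event list is closed, it omits the one event named in the pilot tolerability statement, and it reduces ototoxicity to tinnitus. The plan has no planned, uniform means of counting non-serious hypotension after the bolus.

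The conclusion rests on reading the list as exhaustive and the serious-event rule as nested within it. A more generous reading of the serious-event rule would admit severe cases but would still leave non-serious ones uncounted. The numerical bounds illustrate scale only: they assume zero events and depend on whether the pilot statement covers 54 or 77 patients. The primary analysis is unaffected. This is a cheap improvement to descriptive safety data.

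**What to change.** - Reword the definition so that the list is explicitly open (including but not limited to the named reactions), keeping the 24-hour window.
- Name hypotension and hearing change as events. The investigators should set the thresholds, and should also state the values that count as electrolyte depletion, identically for all sites.
- Abstract blood pressure, potassium and magnesium for the 24 hours after the dose from the medical records already being collected.
- Report each event as a count with an exact 95% interval, described as uncontrolled and descriptive, with the basis for any attribution to furosemide stated.
- When citing the pilot tolerability result, state whether it covers the 54 prospective patients or all 77.

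The cost is protocol wording and a few extra chart fields. No study treatment, visit or sample changes. The downside is more background events for sites to assess and attribute.

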- (2) Patients who die before 14d, and whose serum creatinine remains >2.0 mg/dl over baseline creatinine at the time of death
- (3) Patients who die before 14d and whose urine output is less than 400cc/24 hours at the time of death

Renal Recovery

- (1) Patients who do not require RRT and survive 14d or are discharged prior to 14 days
- (2) Patients who die before 14d with a serum creatinine >2.0 mg/dl above their baseline AND with a urine output >400cc/24 hours

Statistical Analysis

Patients will be followed for 30 days or until hospital discharge, whichever occurs first. Need for dialysis, serum creatinine, urine output, medication regimens, and mortality will be assessed. Primary analysis will be based on the net reclassification index as discussed in the sample size section above, additionally we will look at the more traditional receiver operating characteristics (ROC) of urine output and urinary sediment score and biomarkers after furosemide challenge to predict AKI progression. Additionally, time to AKI progression and renal recovery/non-recovery will be assessed. Patient outcomes will be stratified by entry criteria and baseline renal function. We will be looking at the long term, (3 year) outcomes in this cohort as well. However given the focus of this study is to identify severe AKI early in the clinical course and that rates of morbidity and mortality in our ICU- AKI cohort are extremely high, we are not sufficiently powered to look at long term outcomes and this aspect of the study is somewhat exploratory and will serve as pilot data for future studies.

Study Procedures

1. Identify appropriate patients via inclusion/exclusion
2. Consent patient or legal representative
3. Draw 7cc of blood, collect 50cc of fresh urine
4. Bolus dose of furosemide
5. Assess urine output response over the next 6 hours
6. Match urine output with intravenous isotonic saline, 1 ml for 1 ml for 6 hours (at the discretion of the clinically treating team – if they feel diuresis is needed clinically they can decide to hold the intravenous fluids – this has not changed from prior submission)
7. Draw 7cc of blood, collect 50cc of fresh urine 2 hours after the furosemide
8. Draw 7 cc of blood; and another 50cc of urine the following morning at 24 hours post dose
9. Draw 7 cc of blood; and another 50cc of urine at the time of ICU discharge
10. Draw 7 cc of blood; and another 50cc of urine at the time of hospital discharge

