11. Patient to receive phone call 30 days following the administration of Furosemide – with ascertainment of any recent laboratory samples outside of the University of Chicago
12. Patient to receive phone call 60 days following the administration of Furosemide - with ascertainment of any recent laboratory samples outside of the University of Chicago
13. Patient to receive phone call 90 days following the administration of Furosemide - with ascertainment of any recent laboratory samples outside of the University of Chicago
14. Telephone contact yearly following furosemide administration for 3 years

E. Study Population

The study population will be all patients who develop AKI in the hospital. A wide range of ages over 18 years old and different ethnic background will be included.

Inclusion criteria

- Age: 18 years and older

- Gender: Both
- Increase in serum creatinine of 0.3 mg/dl within 48 hrs or an increase of greater than or equal to 150 to 200 percent from baseline or sustained oliguria (mean output of <0.5 cc/kg/hr for 6 hours).
- Written informed consent
- Patients who already have a indwelling bladder catheter

Exclusion criteria

- Patients under 18-year-old
- Voluntary refusal or missing written consent of the patient or the designated legal representative
- Patients with advanced Chronic Kidney Disease – as defined by a baseline GFR of < 30 ml/min as calculated by the MDRD equation
- Patients with renal transplantation
- Patients with an allergy or sensitivity to loop diuretics
- Patients with a serum K < 3.0 meq/L
- Patients with a serum Mg < 1.0 meq/L
- Patients with a history of hearing loss
- Patients receiving aminoglycosides
- Pregnancy
- Patients with nephrostomy tubes or any type of urinary diversion
- Patients with a clinical syndrome consistent of pre-renal AKI
 - o Defined by fractional excretion of Na of <1% and no evidence of the urinary casts, or
 - o Patients that are under-resuscitated as deemed by treating clinical team, or
 - o Patients who are actively bleeding
- Patients with a clinical syndrome of post-renal AKI
 - o Any radiological study that shows hydro-ureter, or
 - o Clinical scenario wherein urinary obstruction is considered a likely possibility for the cause of AKI

Gender and Minority Inclusions

AKI affects men and women approximately equally, and there is no known racial susceptibility to AKI. Thus, the study is expected to include both male and female subjects, and a significant number of minority subjects.

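### Ear-related harm is recorded only as tinnitus within 24 hours of the bolus, and the plan has no way to ascertain it in patients who cannot communicate in that window

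*Combined protocol and SAP*

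**What the plan says.** Section G (Risks and Side Effects) lists the risks of the study bolus as "hypersensitivity reactions, volume depletion, hypokalemia, hypomagnesemia, and ototoxicity". Its Adverse Events subsection then defines adverse events as furosemide reactions that were absent at baseline. The list is short: allergic reactions, followed by "dehydration, electrolyte depletion and tinnitus occurring within 24 hours post dose administration". Tinnitus is the only ear-related term. Serious adverse events are drawn from treatment-related adverse events, so on a literal reading the same term and window carry over to them.

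The exclusion criteria in Section E include "Patients with a history of hearing loss" and "Patients receiving aminoglycosides". None of the criteria removes a patient who cannot communicate.

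Study Procedures, item 2, reads "Consent patient or legal representative". Section F (Human Subjects) requires two physicians to verify incapacity, "one of whom will be independent of the study team for patients who are unconscious or have documented diagnosis of delirium". It also provides for consent from the subject once he or she can be told of the study.

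Study Procedures schedule blood and urine sampling at 24 hours, at ICU discharge and at hospital discharge. Telephone contacts follow, beginning with item 11: "Patient to receive phone call 30 days following the administration of Furosemide". The stated content of these calls is outside laboratory results. The Long Term Follow-up section adds kidney health, dialysis, hospitalization, death and major renal and cardiac events. Hearing and tinnitus appear in neither place.

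**The concern.** Staff can see a rash, and volume or electrolyte depletion shows in examination or laboratory values. Tinnitus is known only if the patient says so. A patient who is unconscious for the whole 24 hours leaves the same record as one who was asked and had no tinnitus, because the plan has no category for patients who could not be assessed.

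What is at stake is how a later tolerability statement would be read. The Preliminary Studies section already reports that the challenge produced no attributable adverse event in the pilot, without saying how ear symptoms were assessed. If this study ends with few or no tinnitus reports, a reader would naturally set that count against all dosed patients, although only those able to speak could have contributed an event.

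**Working it through.** The documents give no tinnitus rate, expected count or safety denominator, so there is no figure of the plan's own to reproduce. The check has two parts.

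**1. Can the event be observed in every dosed patient?**

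- Harm named: ototoxicity (Section G, list of risks).
- Event recorded: tinnitus, new since baseline, occurring within 24 hours (Section G, Adverse Events).
- Source of information: the patient. No hearing test or scheduled symptom question is described.
- Patients admitted: includes those unconscious or delirious (Section F), with no exclusion for inability to communicate (Section E).
- Later opportunity: consent on regaining capacity, discharge, and the calls at days 30, 60 and 90 all exist, but none asks about tinnitus.

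A patient unable to communicate throughout the window therefore has no planned route by which tinnitus would be recorded. If it were volunteered later, the patient could not date its onset, and its absence at baseline could not be confirmed.

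**2. What would this do to a rate taken over all dosed patients?**

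Let p be the true 24-hour tinnitus rate and f the share unable to report during the window. Assume p is the same in both groups and that inability lasts the full window. Then:

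- number able to report: n = 200(1 − f)
- expected events counted: 200 × p × (1 − f)
- expected rate over all 200: p(1 − f), which is below p whenever p and f exceed zero
- chance of counting no events: (1 − p)^n
- one-sided 95% upper limit for the rate if no events are seen: 1 − 0.05^(1/n)

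Only N = 200 comes from the plan; p and f are assumptions. With p = 1%, the expected number of true cases is 200 × 0.01 = 2.0:

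| f (assumed) | n able to report | Expected counted | Rate over 200 | Chance of no events counted | Upper limit if none seen, over n |
|---|---|---|---|---|---|
| 0% | 200 | 2.0 | 1.00% | 13.4% | 1.49% |
| 10% | 180 | 1.8 | 0.90% | 16.4% | 1.65% |
| 25% | 150 | 1.5 | 0.75% | 22.1% | 1.98% |
| 50% | 100 | 1.0 | 0.50% | 36.6% | 2.95% |
| 75% | 50 | 0.5 | 0.25% | 60.5% | 5.82% |

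Varying p with f fixed at 50%, the chance of counting no events rises from 36.7% to 60.6% when p = 0.5%, and from 1.8% to 13.3% when p = 2%. The last column of the table does not depend on p.

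**The case against.** The strongest reply is that the plan never commits to a biased figure. The Statistical Analysis section contains no adverse event rate, safety population or denominator, and Section G says only that non-serious events go to continuing review. A reader might infer that the plan's ototoxicity rate is too low by construction, or that non-communicating patients are formally counted as event-free. The documents support neither. This objection stands: the bias attaches to a rate or a statement of no events that someone later takes over all dosed patients.

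Second, the 24-hour limit governs when tinnitus occurs, not when it is reported, so an investigator could record tinnitus mentioned on waking. That is correct. But no contact prompts the question and onset could not be dated, so such a record would depend on chance.

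Third, inability to report is certain only for patients unconscious throughout the window. Delirium may come and go, and a state documented at consent need not last 24 hours. This stands and limits how large f can be.

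Fourth, excluding prior hearing loss and current aminoglycosides lowers the true risk. It does, but it does not affect whether an event would be detected.

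Finally, the study's aims are predictive and it has no safety objective. That bears on priority rather than on whether the gap exists.

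**Conclusion.** The concern holds as a gap in ascertainment. For a harm the plan itself names, the only recorded manifestation depends on patient report, the plan admits patients who cannot report, and nothing asks them later. Under the stated procedures, tinnitus in those patients would normally be missed, and any all-patient rate or claim of no events would err downward.

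The direction follows from the text, given some true events among patients unable to report. The size does not, because f and p are both absent from the documents. The figures above are illustrations over assumed ranges and rest on equal risk in the two groups. They should not be read as an estimate of how many events this study will miss.

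This is a minor point about safety reporting. The primary reclassification analysis and the sample size of 200 are unaffected.

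**What to change.** In Section G, for tinnitus only:

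1. At the 24-hour post-dose sampling visit, record whether the patient was able to report symptoms during the window and, if so, ask about new tinnitus. Use this record to define who was assessable. The incapacity documentation in Section F is a poor substitute: it concerns consent at enrolment, it includes conscious, non-delirious patients who may well be able to report a symptom, and it says nothing about status after dosing.
2. Give any tinnitus rate over patients assessable in the window, and state the number not assessable beside it.
3. For those not assessable, ask once about new tinnitus at the first existing contact after they can communicate (consent on regaining capacity, hospital discharge or the day-30 call). List the answers separately as possible events of uncertain onset and attribution, not pooled with the 24-hour events. Patients who never become able to answer remain in the not-assessable count.

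The 24-hour window stays as it is for the other listed events. The cost is one assessability field and one question at contacts already scheduled, with the same wording at all sites, since each conducts and monitors the study independently. The drawback is that late answers are not specific to the study bolus: there is no control arm, and other diuretics or drugs may have intervened. That is why they are listed apart.
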